### 3.3. Sample size

The study's sample size and power analysis was based on the comparisons in Aim 1, the randomized comparisons between arms. The computational notebook that generates all ARRET sample size estimates (primary outcome) and detectable noninferiority margins (secondary outcomes) for Aim 1 is ARRET-sample-size-power.Rmd/.html, located in the same directory as this SAP.

#### 3.3.1. Specific Aim 1: Noninferiority comparisons

Primary outcome: The sample size and power analysis was based on a pairwise comparison of arms. We used a standard sample size calculation for a two-sample t-test. The total sample size required,  $N$ , is approximately:

$$N = \frac{2(Z_{1-\alpha/2} + Z_{1-\beta})^2 S_p^2}{(\mu_1 - \mu_0 - \delta)^2}$$

where  $\mu_1$  and  $\mu_0$  are the average prevalence in treatment and stopping arms and  $\delta$  is the noninferiority margin.  $Z_{1-\alpha/2}$  and  $Z_{1-\beta}$  are from the standard normal distribution for (two-sided) Type I error  $\alpha$  and Type II error  $\beta$ .  $S_p$  is the standard deviation of the outcome (community-level prevalence). Since ARRET is a noninferiority design, we assume that  $\mu_1 - \mu_0 = 0$ , so the formula provides the number of communities required for a given noninferiority margin  $\delta$ .

Since the ARRET trial will condition on prevalence at enrollment, we adjusted the calculation to account for correlation between the baseline measurement and the final endpoint. The adjusted standard deviation accounting for baseline measurement is  $S_r = S_p \sqrt{1 - r^2}$ , where  $r$  is the correlation between outcomes measured at baseline and follow-up.

We assumed a standard deviation of 0.05 (in absolute proportion) for the community level prevalence of *C. trachomatis* infection after one year of treatment, based on previous studies. We also assumed a correlation between baseline and three year values of 0.5, based on previous studies, yielding an effective standard deviation of approximately 0.043.

Under these assumptions, a sample size of  $N = 80$  communities (40 per arm) will provide at least 80% power to detect our desired noninferiority margin of 3%.

Secondary Outcomes: The sample size equation above can be re-arranged to solve for the detectable noninferiority margin given a fixed sample size of  $N = 80$  (with  $\mu_1 - \mu_0 = 0$ , as above):

$$\delta = \frac{\sqrt{2}(Z_{1-\alpha/2} + Z_{1-\beta})S_p}{\sqrt{N}}$$

We estimated the detectable noninferiority margin for secondary outcomes TF prevalence, TI prevalence, and seroprevalence (Pgp3 and CT694 antigens). We informed the calculations for secondary outcomes using data from a cluster randomized trial in Tanzania that collected these measurements from 4,989 children ages 1-9 years from 2012 to 2015.

TF prevalence: We assumed the between-community SD is 0.05 and the correlation between years is 0.5. The residual standard deviation is 0.043 (by coincidence, these assumptions match those for the primary outcome, *C. trachomatis* infection). The detectable noninferiority margin is approximately 3%.

TI prevalence: We assumed the between-community SD is 0.03 and the correlation between years is 0.6. The residual standard deviation is 0.024. The detectable noninferiority margin is approximately 1.7%.

Seroprevalence: We assumed the between-community SD is 0.15 and the correlation between years is 0.75. The residual standard deviation is 0.099. The detectable noninferiority margin is approximately 6.9%.

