## 3.4. Statistical framework

The ARRET trial will use a noninferiority testing framework for the primary and secondary analyses of Aim 1. For each outcome, we will compare measures of trachoma infection (PCR, clinical, serological) between the continuation (azithromycin) arm and the stopping arm. We hypothesize that stopping treatment will be noninferior to the arm that continues treatment, with noninferiority margins specified above in the sample size section, e.g., 3% margin for the primary endpoint of *C. trachomatis* infection.

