## **4. Statistical Principles**

### **4.1. Confidence intervals and *P*-values**

We will construct two-sided 95% confidence intervals to test for noninferiority.

Since the trial has only two measurement times, enrollment and final endpoint, we do not have any interim analyses planned.

We will report 95% confidence intervals on our measures of effect (difference in prevalence) on each secondary outcome. We do not plan to adjust secondary outcome confidence intervals for multiplicity because we expect them to be highly correlated and together they provide corroborating evidence for or against the primary outcome hypothesis.

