Inflammation and active trachoma (TF, TI) as measured by conjunctival photography are dichotomous variables at the individual level, and will yield community-level averages analogous to the primary outcome. The analysis will follow the same methods as described for the primary outcome.

Seropositivity to chlamydia will be measured from dried blood spots, including antibody responses to the antigens Pgp3 and CT694. We will dichotomize antibody responses based on

seropositivity cutoffs established through receiver-operating characteristic (ROC) curve analyses of known positive and negative specimens (conducted at the CDC WHO reference center for trachoma serology). Seropositivity at the individual level will be a dichotomous variable yielding a community-level average of seroprevalence. We will estimate seroprevalence separately by antigen and using the combined response. We will analyze two populations for serologic endpoints. At the community level, we will analyze seroprevalence among children aged 12–36 months (only those born during the duration of the trial) to assess exposure to ocular chlamydia during the study period using a model identical to the primary outcome model. We will also analyze individual-level seropositivity data in the entire age range (1–9 years for serologic measurements) to assess age-seroprevalence curves in children in continuation versus stopping communities. We will additionally estimate the seroconversion rate as measure of force of infection using age-structured seroprevalence using a generalized linear model with a complementary log-log link, age as an offset and treatment arm as a covariate. Since this is an individual-level analysis (rather than community-level), we will estimate standard errors for the model using robust, Huber-White standard errors clustered at the community level.

The trial does not currently include prespecified subgroup analyses.

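### The SAP's secondary noninferiority margins do not follow from its printed formula, whose total N is a per-arm number, and the community-level seroprevalence test in 12-36-month-olds has no margin of its own

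*SAP*

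**What the plan says.** SAP 3.3.1 introduces its formula, 2(Z₁₋α/₂ + Z₁₋β)² S_p² / (μ₁ − μ₀ − δ)², as giving "The total sample size required". For the primary outcome it concludes that 80 "communities (40 per arm) will provide at least 80% power to detect our desired noninferiority margin of 3"%.

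For the secondary outcomes it rearranges the formula to "solve for the detectable noninferiority margin given a fixed sample size of" 80, printing S_p rather than the baseline-adjusted S_r. It then lists, with residual SDs:

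- TF: SD 0.05, r 0.5, residual 0.043, margin about 3%.
- TI: SD 0.03, r 0.6, residual 0.024: "The detectable noninferiority margin is approximately 1.7"%.
- Seroprevalence: SD 0.15, r 0.75: "The residual standard deviation is 0.099. The detectable noninferiority margin is approximately 6.9"%.

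These inputs are attributed to a Tanzanian cluster-randomized trial in children aged 1-9 years. SAP 3.4 applies a noninferiority framework to the primary and secondary analyses, "with noninferiority margins specified above in the sample size section". SAP 4.1 fixes the interval: "We will construct two-sided 95% confidence intervals to test for noninferiority".

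SAP 6.2.1 (Aim 1) places the community-level seroprevalence comparison in children aged 12-36 months, "using a model identical to the primary outcome model". The serology analyses over the whole 1-9-year range are individual-level: age-seroprevalence curves and a seroconversion-rate model.

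**The concern.** For the TF, TI and serology comparisons, the sample-size section is the only source of a margin. SAP 6.2.1 relates the primary 3% to the 5% TF programme threshold, but no comparable rationale is given for the secondary figures. If the calculation does not produce them, they have no visible basis, and a wider margin makes noninferiority easier to declare.

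For serology there is a second gap. The margin was apparently worked out for one age range, and the community-level test is run in a much narrower one with far fewer children per community. A reader who applied 6.9% to that test would be using a threshold that was never derived for it.

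**Working it through.** **Inputs.** Two-sided α 0.05 (SAP 4.1), 80% power, 40 communities per arm, and the SDs and correlations in SAP 3.3.1. Power is stated only for the primary outcome; I assume that 80% carries over to the secondary margins. Z sum = 1.960 + 0.842 = 2.802.

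**Residual SDs**, S_r = S_p√(1 − r²):
- TF: 0.05 × √0.75 = 0.0433
- TI: 0.03 × √0.64 = 0.0240
- Serology: 0.15 × √0.4375 = 0.0992

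All three reproduce the SAP.

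**What N means.** For the primary outcome, 2 × 2.802² × 0.0433² / 0.03² = 32.7. This is the usual per-arm number for comparing two means; a total would carry 4 in place of 2. With 40 per arm, SE = 0.0433 × √(2/40) = 0.00968 and power = Φ(0.03/0.00968 − 1.96) = 87%. That agrees with the SAP's claim of at least 80%.

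**Detectable margins**, δ = √2 × 2.802 × S / √N:

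| Reading | TF | TI | Serology |
|---|---|---|---|
| N = 80, S_p as printed | 2.2% | 1.3% | 6.6% |
| N = 80, S_r | 1.9% | 1.1% | 4.4% |
| N = 40 per arm, S_p | 3.1% | 1.9% | 9.4% |
| N = 40 per arm, S_r | 2.7% | 1.5% | 6.2% |
| N = 33 per arm, S_r | 2.99% | 1.66% | 6.84% |
| N = 32 per arm, S_r | 3.03% | 1.68% | 6.95% |
| **Stated in SAP** | **3%** | **1.7%** | **6.9%** |

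No reading at N = 80 or 40 per arm with 80% power gives the stated set. It matches about 32-33 per arm. Equivalently, it is the primary 3% scaled by residual SDs: 3% × 0.0240/0.0433 = 1.7% and 3% × 0.0992/0.0433 = 6.9%.

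With 40 per arm, power at the stated margins is 87% (TF), 89% (TI) and 87% (serology). The excess over the 80%-power values is 1.7/1.503 = 1.13 for TI and 6.9/6.22 = 1.11 for serology.

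**Serology at 12-36 months.** Protocol 4.1.2 samples 40 children aged 1-9 years per community for dried blood spots. If ages are spread evenly (assumption), 40 × 24/108 = 8.9 are aged 12-36 months. The documents give no prevalence, SD or correlation for this band, so the following only illustrates the range. Take the observed SD as √(b² + p(1 − p)/8.9), with p the true prevalence and b the true between-community SD:

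- p = 2%, b = 0.02, r = 0.5: observed SD 0.051, residual 0.044, detectable margin 2.8%.
- p = 15%, b = 0.10, r = 0: SD 0.156, detectable margin 9.8%.

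What a 6.9% margin would let through was checked by simulation: beta-binomial counts, 9 children per community, 40 communities per arm, true SD 0.02 or 0.03, each arm with its own variance, no baseline adjustment, 20,000 runs. A rise from 3% to 6% passes in about 64-67% of trials. This falls to about 52% if the third scenario of SAP Figure 1 also applies (a lower limit above zero counts as inferior). A rise from 5% to 10% passes in about 16%.

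**The case against.** Several counter-arguments have force.

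- **The stated margins err on the side of more power.** At 40 per arm each has 87-89% power. TF at 2.7% is compatible with approximately 3%, and the TI and serology gaps are 0.2 and 0.7 percentage points. This stands, so the arithmetic part concerns traceability and modestly loose margins.
- **The notebook may explain the figures.** SAP 3.3 cites a companion notebook, which may use a different n or power. It is not among the documents. The SAP text should still reproduce on its own, because SAP 3.4 relies on it.
- **The secondary results are supportive.** SAP 4.1 reports them as 95% intervals that corroborate the primary result. But SAP 3.4 expressly applies noninferiority margins to them.
- **The age mismatch is partly inferred.** SAP 3.3.1 gives the source data's age range but does not repeat it beside SD 0.15 and r 0.75. Protocol 7.1 describes an age-stratified sample, so 9 of 40 is only an approximation.

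A reader might infer that mislabelling N leaves the trial underpowered. The documents do not support this: the formula needs 33 per arm and the design has 40. A reader might also infer that the SAP assigns 6.9% to the 12-36-month test. No sentence does so; SAP 6.2.1 carries over the primary model, and SAP 3.4 refers to margins only in general. The supportable statement is that no margin is derived for that comparison.

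**Conclusion.** The formula is mislabelled, and the rearranged version as printed gives none of the three secondary margins. TI and serology are about 13% and 11% wider than 40 per arm supports at 80% power; TF is within rounding. This assumes that the 80% power stated for the primary outcome was meant for the secondary outcomes too. The primary sample size and its power are unaffected.

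For serology, the one community-level comparison lacks a margin. Whether 6.9% would be too loose or unattainable there cannot be settled from the documents: the range of about 3% to 10% rests on assumed prevalences of 2-15%, between-community SDs of 0.02-0.10, baseline correlations of 0-0.5 and an even age spread. The simulated pass rates are likewise illustrations, not predictions. This should be corrected, but it does not threaten the primary conclusion.

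**What to change.** 1. In SAP 3.3.1, define N as communities per arm and print S_r in the rearranged formula.
2. Restate the detectable margins as 2.7% (TF), 1.5% (TI) and 6.2% (serology) at 80% power with 40 per arm, or keep 3/1.7/6.9% and state that they correspond to about 87-89% power. Either way these are detectable differences. If SAP 3.4 keeps them as decision margins, a sentence on why each is an acceptable loss would help, since detectability alone does not show that.
3. State that 6.9% does not apply to the 12-36-month comparison. Before unmasking, either derive a margin from that age group's own SD, baseline correlation and number of children, or report the difference and its 95% interval without a noninferiority verdict.

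The cost is SAP wording and a rerun of the sample-size notebook. No additional children or communities are needed; some secondary margins may become slightly tighter. A margin chosen after unmasking would not be credible, so the timing matters.

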### 3.3.2. Specific Aim 2: Hidden Markov Models

Standard formulas for sample size estimation for hidden Markov methods are not available, but the proposed sample size can be evaluated by examination of the precision of standard sensitivity and specificity calculations (Accuracy in Parameter Estimation). Assuming 5% of the population will exhibit true positivity for a given test, we anticipate 100 true positives and 1,900 true negatives. These sample sizes provide a margin of error of approximately 4.2% for sensitivity and 0.1% for specificity (assuming true sensitivity and specificity of approximately 95%). We anticipate no loss of precision resulting from the use of the combined hidden Markov approach.

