2.3.3 SAMPLE SIZE

40 communities per arm (80 total) will be included in the study. Please see Statistical Analysis Plan (SAP) for same size calculation details.

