4.1.2 MONITORING ELIGIBILITY

Monitoring will be based on population-based samples. The following groups will be monitored at each study visit: 1) a random sample of 50 children aged 0-9 years will receive conjunctival photography and swabbing; 2) a random sample of 40 children aged 1-9 years will receive dried blood spot collection. Eligibility for these groups will be based on the previous census.

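### SAP 3.3.2 states a specificity margin of error of 0.1%, but its own inputs give about 1.0%; the implied 2,000 children also do not match the serology sample of 1,600 per arm per visit

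*SAP*

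**What the plan says.** SAP 3.3.2 notes that hidden Markov methods have no standard sample size formula, and checks the proposed size through the precision of ordinary sensitivity and specificity estimates. It starts from a prevalence ("Assuming 5% of the population will exhibit true positivity for a given test"), turns this into counts ("we anticipate 100 true positives and 1,900 true negatives"), and concludes: "These sample sizes provide a margin of error of approximately 4.2% for sensitivity and 0.1% for specificity". The parenthesis that follows gives the accuracy used: "assuming true sensitivity and specificity of approximately 95" per cent. The section ends: "We anticipate no loss of precision resulting from the use of the combined hidden Markov approach".

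The sampling plan is set out elsewhere. Protocol 2.3.3 says "40 communities per arm (80 total) will be included in the study". Protocol 4.1.2 and SAP 5.1 give 50 children aged 0-9 years per community for swabs and photographs. For serology, Protocol 4.1.2 says "a random sample of 40 children aged 1-9 years will receive dried blood spot collection". SAP 6.2.1 (Aim 2 Analysis) counts seropositivity among the tests in the model, analyses the two arms separately, works at community level, and treats no test as the reference standard.

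**The concern.** The two stated margins cannot both come from one calculation. Sensitivity and specificity are given the same assumed value, so the margins can differ only through the counts. A 19-fold larger count cannot shrink a margin 42-fold.

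This section is the only precision justification offered for Aim 2, so a reader has nothing else from which to judge how well false positives are controlled. At 5% true positivity, 95% of children are true negatives, and a one-point change in specificity moves the apparent positivity of a single test by 0.95 points. A margin of 0.1% invites the reader to ignore false positives; a margin of 1.0% does not.

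Two smaller matters sit beside it. The count of 2,000 is applied to any given test, although serology samples fewer children. The closing sentence on precision has no derivation behind it.

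**Working it through.** **Inputs**

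- True positives 100, true negatives 1,900, sensitivity and specificity 0.95, positivity 5%: SAP 3.3.2.
- Confidence level: SAP 3.3.2 states none. Two-sided 95% is assumed here, as in SAP 4.1 ("We will construct two-sided 95% confidence intervals to test for noninferiority").
- 40 communities per arm: Protocol 2.3.3. Children per community: 50 for swabs and photographs, 40 for blood spots: Protocol 4.1.2.

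**Step 1. Reproduce the sensitivity figure.** Margin = z × sqrt(p(1 − p)/n), with p(1 − p) = 0.95 × 0.05 = 0.0475.

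1.96 × sqrt(0.0475/100) = 1.96 × 0.0218 = 0.0427, or 4.27%. The SAP prints 4.2%. This identifies the method.

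**Step 2. Apply the same formula to specificity.**

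1.96 × sqrt(0.0475/1900) = 1.96 × 0.0050 = 0.0098, or 0.98%. The SAP prints 0.1%. The ratio is about 9.8.

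**Step 3. A check that needs no confidence level.** With the same p and z, the two margins must stand in the ratio sqrt(1900/100) = 4.36. The stated ratio is 4.2/0.1 = 42. Starting from the SAP's own 4.2%, specificity should be 4.2%/4.36 = 0.96%.

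**Step 4. Look for a reading that rescues 0.1%.** Specificity margin at p = 0.95:

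| Variant | Margin |
|---|---|
| z = 2, n = 1,900 | 1.00% |
| Wilson, n = 1,900 | 0.98% |
| Clopper-Pearson, n = 1,900 | 1.01% |
| Continuity-corrected, n = 1,900 | 1.01% |
| 90% interval, n = 1,900 | 0.82% |
| One standard error, n = 1,900 | 0.50% |
| Both arms, n = 3,800 | 0.69% |
| Both arms and both visits, n = 7,600 | 0.49% |

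None comes near 0.1%. Reaching it at 95% specificity would need 1.96² × 0.0475/0.001² ≈ 182,500 true negatives. With 1,900 true negatives it would need a specificity of about 99.95%, against the 95% in the same sentence.

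**Step 5. Where 2,000 comes from.** 100 + 1,900 = 2,000 = 40 × 50, which is one arm at one visit and fits the separate analysis by arm. For blood spots, 40 × 40 = 1,600 per arm per visit. Across both arms the totals are 4,000 and 3,200 per visit.

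**Step 6. Serology margins, if 5% positivity is carried over.** The counts become 0.05 × 1,600 = 80 and 0.95 × 1,600 = 1,520.

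- Sensitivity: 1.96 × sqrt(0.0475/80) = 4.78%.
- Specificity: 1.96 × sqrt(0.0475/1520) = 1.10%.

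The documents give no mean seroprevalence. SAP 3.3.1 assumes a between-community SD of 0.15 for it, three times that for infection, so a 5% mean is doubtful. At an assumed 20% the counts are 320 and 1,280, and the margins are 1.96 × sqrt(0.0475/320) = 2.4% and 1.96 × sqrt(0.0475/1280) = 1.2%.

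**The case against.** The best defence is that nothing in the trial depends on this number. SAP 3.3 bases the sample size on Aim 1, and SAP 3.3.2 offers the calculation only as a stand-in where no formula exists. No threshold, model input or decision rule uses the 0.1%. That is true. It limits the consequence but does not make the figure right.

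On serology, the SAP never names it beside the 2,000. The link comes from the reference to a given test in SAP 3.3.2, together with the list of tests in SAP 6.2.1. The effect is also modest: 4.3% to 4.8%, and 0.98% to 1.10%. This stands, and the serology point is therefore secondary. A reader might also infer that the whole trial has only 1,600 blood spot samples; that count is per arm per visit.

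Three stronger readings are tempting, and the documents do not support them.

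- **Clustering.** One could build a design effect from the assumed SD of 0.05 for community infection prevalence and widen the specificity margin. That SD describes variation in infection between communities, not variation in test errors among uninfected children. The documents give no figure for the latter. All that can be said is that the margins treat children as independent.
- **Elimination.** One could argue that a 1% margin prevents Aim 2 from telling low infection from none. SAP 6.2.1 describes no step that feeds this margin into the model, and the documents give no infection level for such a comparison.
- **Wider model intervals.** One could say that the hidden Markov intervals must be wider than these margins. The target is hidden prevalence estimated from several indicators, and neither the documents nor the working above settle how its precision compares. The supportable criticism is that the SAP's opposite claim is unsupported: its calculation takes true status as known, while the model does not.

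**Conclusion.** Wrong as written. The specificity margin in SAP 3.3.2 should be about 1.0% (0.98%), roughly ten times the printed value. The result rests on the SAP's own counts and assumed accuracy, and on a 95% level that the section does not state but that reproduces its sensitivity figure. The ratio check reaches the same answer without that assumption. The pattern is consistent with a misplaced decimal point.

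The serology mismatch is real but small. Its margins of 4.8% and 1.1% hold only if 5% positivity also applies to serology. The statement on precision lacks a basis; it has not been shown to be false.

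A reader might infer that the trial is undersized. It does not follow: the 80 communities rest on the Aim 1 comparison, which this error does not touch.

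**What to change.** Amend SAP 3.3.2 and log the change in the SAP revision history:

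1. Restate the margins, for example: *about 4.3% for sensitivity and 1.0% for specificity (95% level; 2,000 children per arm per visit, treating children as independent)*.
2. Add that serology has 1,600 children per arm per visit, with margins of about 4.8% and 1.1% if 5% positivity is assumed, or give the expected seroprevalence and recompute.
3. Delete the closing sentence on precision, or support it, for example with a simulation of the planned model.

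Items 1 and 2 cost wording only, and the stated specificity precision becomes less favourable. Item 3 costs nothing if the sentence is deleted, and some simulation work if it is kept. Sample size, sampling and the Aim 1 analysis do not change.

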8.8 FIELD GRADING AND CLINICAL PHOTOGRAPHY

The same random sample of 50 children <10 years old who will undergo conjunctival swabbing will also undergo conjunctival photography and trachoma field grading. Four specific team members will be designated as photographers for the entire trial to ensure high quality photographs by an experienced photographer.

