### **6.2.1. Aim 2 Analysis: Hidden Markov Model for Infection Prevalence**

The primary analysis for Specific Aim 2 will be a hidden Markov model, conducted at the community level using a truncated normal distribution. Analyses will be conducted in the continuation and stopping arms separately, as distribution of azithromycin likely affects the relationship between the indicators. This will allow for understanding of the best tools for surveillance both with and without azithromycin treatment. This model will use four diagnostic tests – TF, TI, ocular chlamydia, and seropositivity to CT694 and Pgp3 separately, and will not assume that any of the tests are a gold standard. The truncated normal distribution allows several options to handle the expected high density of communities with zero prevalence, including zero-inflation or a free fitted parameter. The model will incorporate delays in TF and serology, as TF follicles can take months or longer to recede and serologic measurements are long-lasting. The hidden Markov model will be fit to the prevalence of the indicators for trachoma transmission to estimate the prevalence of the true hidden prevalence of trachoma. For the test of treatment, we will assess the effect of continuation versus stopping on alternative indicators alone and in combination. Absence of an effect of treatment will suggest that there is no true infection in the community. In practice, we have found some degree of model exploration necessary, and our publications will include all explored models. Estimation will be conducted using the standard Metropolis algorithm (as we have conducted before).

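### The Aim 2 precision in SAP 3.3.2 assumes children of known true status; the Aim 2 model has no gold standard and, as written, does not identify sensitivity or the scale of hidden prevalence

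*SAP*

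**What the plan says.** SAP section 3.3.2 notes that no standard sample-size formula exists for hidden Markov methods, so it uses ordinary sensitivity and specificity precision as a stand-in. Its inputs are:

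- prevalence: "Assuming 5% of the population will exhibit true positivity for a given test"
- counts: "we anticipate 100 true positives and 1,900 true negatives"
- accuracy: "assuming true sensitivity and specificity of approximately 95"%

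The printed margins are about 4.2% for sensitivity and 0.1% for specificity. The section closes with "We anticipate no loss of precision resulting from the use of the combined hidden Markov approach".

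SAP section 6.2.1 (Aim 2) describes the analysis itself. It is "conducted at the community level using a truncated normal distribution", run separately in each arm, and it "will not assume that any of the tests are a gold standard". On the data used: "The hidden Markov model will be fit to the prevalence of the indicators for trachoma transmission to estimate the prevalence of the true hidden prevalence". The indicators are TF, TI, PCR, Pgp3 and CT694. Zero-inflation or a free parameter is offered as an option for communities at zero, and delays in TF and serology are to be included. Estimation is by the Metropolis algorithm, some model exploration is expected, and all explored models are to be published.

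Protocol 8.8 says of the data collected: "The same random sample of 50 children <10 years old who will undergo conjunctival swabbing will also undergo conjunctival photography and trachoma field grading".

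**The concern.** The two sections describe different analyses. The precision statement needs individual children and known truth. The model uses community prevalences and has no known truth. Both differences cost information, so a claim of no loss needs a simulation or an argument, and the SAP gives neither.

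At stake are how well Aim 2 can say what level of infection lies behind the indicators, and how well each indicator detects it. If the data do not fix the scale, Metropolis sampling will still return an interval, but its width in that direction will reflect whatever prior or constraint was chosen. A reader of section 3.3.2 would expect a few points of data-driven precision.

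**Working it through.** **Inputs.** 40 communities per arm (Protocol 2.3.3); 50 children per community for swabs and photographs and 40 for blood spots (Protocol 4.1.2); 5% positivity, 100 positives, 1,900 negatives, sensitivity (Se) and specificity (Sp) 95% (SAP 3.3.2). The SAP gives no confidence level for these margins; 95% two-sided is assumed.

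**Step 1: reproduce the printed margins.** Half-width = 1.96 × √(p(1−p)/n), with p = 0.95.

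- Se, n = 100: 1.96 × √(0.0475/100) = 4.27 points. This agrees with the printed 4.2% to rounding or truncation.
- Sp, n = 1,900: 1.96 × √(0.0475/1,900) = 0.98 points. The printed 0.1% is about ten times too small; it would need about 182,500 negatives.
- 100 + 1,900 = 2,000 = 40 × 50, which is one arm at one visit for PCR, TF and TI. Serology has 40 × 40 = 1,600; at 5% that is 80 positives and 1,520 negatives, with margins of 4.78 and 1.10 points.

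**Step 2: effect of moving to community level, truth still known.** Illustration: 4,000 simulations of 40 communities × 50 children, beta-distributed prevalence with mean 5%, and least-squares regression of test prevalence on the sample's true prevalence. The 95% half-width for sensitivity is about ±17 points with between-community SD 0.05 and ±19 to 20 with SD 0.039. With 80 community-visits it is ±12 to 14. The SAP does not propose this regression; it only shows the cost of aggregation.

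**Step 3: effect of removing the known truth.** With a linear test response, test j in community i has expected prevalence

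(1 − Sp_j) + (Se_j + Sp_j − 1) × π_i,

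where π_i is hidden prevalence. Multiply every π_i by k and divide every (Se_j + Sp_j − 1) by k: nothing observable changes. With Sp = 95%:

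| k | hidden prevalence | Se = 0.90/k + 0.05 | observed prevalence |
|---|---|---|---|
| 1 | 5% | 95% | 0.05 + 0.90 × 0.05 = 9.5% |
| 1.5 | 7.5% | 65% | 0.05 + 0.60 × 0.075 = 9.5% |
| 2 | 10% | 50% | 0.05 + 0.45 × 0.10 = 9.5% |

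Five indicators do not help. The means and covariances of five community prevalences involve 12 parameters (latent mean and variance, five slopes, five intercepts) but have rank 10; location and scale are free.

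A zero-inflated, zero-truncated normal for π (illustrative mean parameter 0.04, SD parameter 0.05, 30% zeros) can anchor the location but not the scale. Sensitivities of 95%, 65%, 50% and 35%, with mean hidden prevalence 4.1%, 6.1%, 8.2% and 12.3%, gave the same likelihood. Also truncating at 1 altered it only from about the seventh digit.

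**Step 4: what child-level data could give without a gold standard.** Latent-class Fisher information, 2,000 children, tests independent given true status, no clustering, Se = Sp = 95%. Sensitivity half-widths in points:

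| true prevalence | truth known | 3 tests (PCR, TF, TI) | 5 tests |
|---|---|---|---|
| 5% (100 positives) | 4.3 | 6.5 | 4.5 |
| 2% (40) | 6.8 | 14 | 7.3 |
| 1% (20) | 9.6 | 26 | 10.5 |

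The five-test column is a favourable bound. It needs blood spots from the same 2,000 children, whereas only 1,600 are sampled and the documents do not say they are the swabbed children. It also treats the two antigens as independent.

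**The case against.** The strongest reply is that Step 3 analyses a simpler model than the SAP's: static, linear, with free parameters and no prior. The SAP describes a hidden Markov model with delays, fitted by Metropolis as in earlier work it cites. A nonlinear transmission model, an informative prior or one fixed sensitivity could supply the scale, and these may exist in sources not available here. That stands. A reader might infer that the approach can never determine sensitivity or prevalence; the documents support only that the SAP does not state what would identify them.

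Second, the Aim 2 hypothesis in SAP section 2.2 is that the interval for true infection includes zero. Under rescaling, zero stays zero. Section 6.2.1 also plans a treatment comparison on the indicators themselves, which needs no sensitivity estimate. That stands too, so it would be wrong to infer that Aim 2 as a whole fails.

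Third, sensitivity is a planning proxy in section 3.3.2, not a named estimand, and SAP section 3.3 bases the sample size on Aim 1. This limits the consequence. It does not make the closing sentence true.

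Fourth, the wide three-test margins at 1% and 2% owe much to low prevalence and the omission of serology. They are not general figures for the loss from lacking a gold standard.

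**Conclusion.** The concern holds in a limited form. The no-loss sentence is unsupported: the 4.2% needs 100 children of known status, and the written model has neither child-level data nor known status. Aggregation alone widens the sensitivity margin to roughly ±17 to 20 points for 40 communities under the illustrative assumptions. With truth latent, a linear response and no outside information, sensitivity and the scale of hidden prevalence have no finite margin.

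The zero point is less affected because truncation or zero-inflation can anchor it, although the SAP leaves the handling of zeros open. Aim 1 and the sample size are unaffected.

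Two stronger readings fail. The printed precision does not simply belong to 2,000 children of known status: sensitivity matches that calculation, but specificity would be 0.98%, not 0.1%. Nor do the documents require abandoning the community-level model. Visits are repeated cross-sections, so the community is the unit that persists between them, and a child-level model has its own assumptions. The choice of level is a trade-off; the precision statement and the missing constraint are the faults.

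**What to change.** 1. In SAP 3.3.2, delete the no-loss sentence.
2. Replace the 4.2% and 0.1% with simulated precision of the model actually fitted: 40 communities per arm, 50 children for PCR, TF and TI, 40 for serology, with between-community variation, at true prevalences of 1%, 2% and 5%. If a known-truth figure is kept for reference, specificity should read about 1.0%.
3. In SAP 6.2.1 (Aim 2), prespecify what sets the scale: a fixed value or a stated informative prior for at least one test's sensitivity. Report hidden prevalence as conditional on it.
4. Add, as a supporting analysis, a child-level latent-class model of the PCR, TF and TI results already collected on the same children.

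The cost is SAP wording, a simulation and some model code, with no new visits, samples or participants. The stated precision will look less favourable. The child-level analysis must assume the tests are independent given true status: three tests in one population give 2³ − 1 = 7 free cell probabilities for 7 parameters (one prevalence, three sensitivities, three specificities), so a TF–TI dependence term could not be added without further information, such as variation between communities.
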